#### 2 AMENDMENTS FROM PREVIOUS VERSION(S)

2.0	16-September- 2024	Amended	3.1 Study Design	Sample size updated
	2027	Amended	7.3 Additional exploratory analysis	
 
Additional analyses:
 
Stratified analysis of Paxlovid prescription at index by demographic and clinical characteristics
 
Stratified analysis of HCRU (Healthcare Resource use) at index date by demographic and clinical characteristics.
 
Examine the association between patients' hospitalization due to COVID-19 related reasons and Covariates*, using logistic regression model at the index date.
 

		Amended	9. List of tables and Table shells	As per additional exploratory analyses, list of tables updated, and corresponding table shells added in the excel. The analysis already performed influenced amendment mentioned in the section 7.3

#### **3** INTRODUCTION

Note: in this document, any text taken directly from the non-interventional (NI) study protocol is *italicised*. The protocol version 1.0 dated on 17 March 2023 was used to develop the SAP.

#### Background

Coronaviruses are a group of viruses of zoonotic origin, of which seven species have been identified thus far as infectious to humans. In December, 2019, clusters of patients with idiopathic pneumonia were identified in Wuhan, China, with clinical presentation including fever, cough, dyspnea, and chest discomfort. A novel coronavirus sequence was isolated from the cluster of patients, termed severe acute respiratory syndrome coronavirus 2 (SARS-CoV-2), with the associated respiratory disease termed COVID-19. By January 30th, 2020, the World Health Organization (WHO) declared COVID-19 a Public Health Emergency of International Concern (PHEIC) due to rapid community transmission via respiratory droplets, leading to an exponential surge in the number of cases and severity, especially in a context where knowledge on this novel virus' epidemiology and potentiality was scarce. COVID-19 was declared as a pandemic on 11 March 2020, and as of February 2023, more than 679 million cases and 6.8 million deaths have been confirmed globally in 228 countries and territories.

COVID-19 clinical presentation and severity is vastly heterogenous, whereby patients may experience asymptomatic infection, mild illness, moderate illness, severe illness, or critical illness requiring hospitalization. Common symptoms include cough, fever, dyspnea, fatigue, sore throat, anosmia, and nausea. Critical illness is characterized by severe respiratory failure, systemic inflammatory response, septic shock, and multi-system dysfunction and failure, including the cardiovascular system, central nervous system, gastrointestinal system, renal system, and skin. Recent data related to COVID-19 symptom severity have revealed that approximately 80% of cases are mild-to-moderate, 15% are severe, and 5% are critical. Whilst the majority of cases are indeed asymptomatic or mild, COVID-19 patients who are hospitalized due to infection are at great risk of prolonged disease, complications, increased hospital length of stay (LOS), high morbidity and mortality.

Based on the most recent treatment guidelines put forth by the National Institutes of Health (NIH), management of non-hospitalized adults with acute COVID-19 infection includes supportive care (e.g., adequate hydration, rest, monitoring body temperature, and taking antipyretics and analgesics to reduce symptom severity), advice on reducing viral transmission, and advice on when to seek healthcare provision or in-person evaluation. Adults that do not require hospitalization or supplemental oxygen yet are at high-risk of disease progression to severe/critical illness (eg, patients with malignancies, neurological diseases, hypertension, diabetes mellitus, obesity, and immunocompromised conditions), may additionally receive antiviral therapy to reduce risk of progression, hospitalization, or death. Current COVID-19 antiviral therapeutic options, in order of preference, include ritonavir-boosted nirmatrelvir (PaxlovidTM) or remdesivir.

*Molnupiravir may additionally be considered as an alternative therapeutic option only when the aforementioned are unavailable, infeasible, or clinically inappropriate to use.*

The Saudi MoH Protocol for Patients Suspected of/Confirmed with COVID-19 Supportive care and antiviral treatment of suspected or confirmed COVID-19 infection (Version 3.7) September 29th, 2022 follows the same guidance described above.

Nirmatrelvir, ritonavir is an antiviral therapy consisting of two active substances that reduce the ability of SARS-CoV-2 to multiply in the body, and thus prevent disease progression. The first active substance, nirmatrelvir (PF-07321332), works by blocking viral enzyme activity and subsequent multiplication. The second active substance, ritonavir, delays breakdown of nirmatrelvir; thus, maintains sufficient levels of nirmatrelvir in the body to allow it to continue its effect on reducing viral multiplication. Nirmatrelvir, ritonavir should be initiated after confirmed COVID-19 diagnosis and within 5 days of symptom onset; administered as 300 mg of nirmatrelvir (two 150 mg tablets) with 100 mg ritonavir (one 100 mg tablet) together, every 12 hours, for 5 days. Based on the guidelines put forth by the Center for Disease Control and Prevention (CDC), COVID-19 patients who are at high-risk of disease progression to severe COVID-19 include patients aged >50 years, those who are unvaccinated or incompletely vaccinated, in addition to specific underlying medical conditions including asthma, cancer, chronic lung diseases, chronic liver diseases, Diabetes mellitus, and Down's syndrome.

Nirmatrelvir, ritonavir EUA was based on data from an interim analysis of a Phase II-III randomized, double-blind, placebo-controlled clinical trial in non-hospitalized adult patients with a confirmed COVID-19 diagnosis, who were symptomatic, and had at least *1* risk factor for progression to severe disease. Interim analysis results from this trial, titled "Evaluation of Protease Inhibition for COVID-19 in High-Risk Patients (EPIC-HR)" (NCT04960202), revealed 89% reduced risk of COVID-19-related hospitalization and 28-day mortality among the Paxlovid group compared to the placebo group. A meta-analysis on the efficacy and safety of nirmatrelvir, ritonavir for COVID-19 treatment has additionally shown an Overall 78% reduction in COVID-19-related mortality and hospitalization. Whilst the trial was conducted prior to the emergence of the SARS-CoV-2 omicron variants, recent studies in real-world settings have shown that nirmatrelvir, ritonavir is also effective against these variants. Other COVID-19 antiviral therapies with reported risk reduction of hospitalization or death include remdesivir (87% reduced risk), sotrovimab (85% reduced risk), and molnupiravir (50% reduced risk). Sotrovimab is no longer authorized to treat COVID-19 in any United States of America (USA) region due to increases in the proportion of COVID-19 cases caused by the Omicron BA.2 sub-variant. Bebtelovimab has also been authorized for emergency use, and available data from the BLAZE-4 clinical trial have revealed reduced viral load and improvement in symptoms, however, no clinical efficacy data of patients at risk of progressing to severe COVID-19 is available vet. Since November 2022 bebtelovimab is not currently authorized for emergency use in the USA because it is not expected to neutralize Omicron subvariants BO.1 and BO.1.1.

> PFIZER CONFIDENTIAL CT24-WI-GL03-RF03 2.0 Non-Interventional Statistical Analysis Plan 01-Jun-2020 Page 8 of 42

Real-world studies assessing nirmatrelvir, ritonavir effectiveness and health impact are limited, and there are no studies yet that assess patients' treatment patterns. A real-world study conducted in Israel among high-risk patients showed nirmatrelvir, ritonavir to be highly effective, and was significantly associated with reducing the rate of progression to severe COVID-19 and COVID-19-specific mortality. Another study conducted in Hong Kong to assess the effectiveness of molnupiravir and nirmatrelvir, ritonavir during the Omicron BA.2 variant of COVID-19 among patients initially not requiring oxygen therapy revealed shorter time to achieve lower viral load, lower risk of disease progression, reduced hospital LOS, and lower risk of all-cause mortality. In Shanghai, China, results from a study assessing nirmatrelvir, ritonavir among immunocompromised inpatients further revealed treatment effectiveness in terms of faster viral load clearance, and shorter time to viral elimination, with patients having better prognosis when treatment was initiated  $\leq 5$  days following COVID-19 diagnosis.

Several countries have incorporated nirmatrelvir, ritonavir within their national COVID-19 treatment protocols after regulatory body approval for emergency use, including the USA, several countries in Europe including the United Kingdom, and European Union (EU) countries including Italy, Germany, and Belgium, and the Middle East and North Africa (MENA) region, including the KSA and Bahrain. Moreover, it is expected that additional countries will adopt the use of nirmatrelvir, ritonavir within their protocol as it becomes more readily available, particularly considering near-future decentralization and generic production of nirmatrelvir, ritonavir across a larger number of countries, including low- and middle-income countries.

#### Rationale

The COVID-19 pandemic has exacerbated healthcare systems globally, with dire repercussions on patients, healthcare infrastructure, resources, and finances. Although COVID-19 patient characteristics and disease course in healthcare settings have been described in the literature since the beginning of the pandemic in various regions including the USA, EU, and the MENA region; there is limited data related to COVID-19 patient characteristics, treatment patterns, and HCRU identified in an outpatient setting, particularly in the MENA region. One study reported that among other factors such as age, male gender, and underlying medical conditions; being of Arab ethnicity was associated with increased risk of severe COVID-19 and related mortality.

In KSA, nirmatrelvir, ritonavir has been approved and conditionally registered by the Saudi Food and Drug Authority (SFDA) for patients aged  $\geq 12$  years, weighing  $\geq 40$  kg with mild-to-moderate COVID-19 symptoms and at high-risk for progression to severe COVID-19 infection. The availability of antiviral therapies such as nirmatrelvir, ritonavir in an outpatient setting has the ability to reduce disease progression, hospitalization, and COVID-19-related mortality, when eligible patients are treated. With the current EU authorization and subsequent use of nirmatrelvir, ritonavir, there is a need to generate -RWE during this early EUA utilization phase to inform decision-making on national levels.

PFIZER CONFIDENTIAL CT24-WI-GL03-RF03 2.0 Non-Interventional Statistical Analysis Plan 01-Jun-2020 Page 9 of 42 As such, this study aims to describe the baseline demographic, clinical characteristics, and HCRU of adult COVID-19 patients who have been prescribed nirmatrelvir, ritonavir treatment in KSA.

#### 3.1 STUDY DESIGN

This is a multi-center, retrospective observational study that will be conducted in KSA. The aim of this study is to capture data on the baseline demographic, clinical characteristics, and HCRU of adult COVID-19 patients who have been prescribed nirmatrelvir, ritonavir treatment.

An overview of the study design is depicted in Figure 1. The sample size for this study depends on the number of COVID-19 patients visiting the selected sites, in addition to nirmatrelvir, ritonavir prescription practices by the treating physician in line with local prescription guidelines in KSA. However, based on feasibility assessments, the minimum target sample size for the study is approximately 250 evaluable patients across 3 sites in KSA. The study will aim to meet this target sample size with a single Cohort of patients identified retrospectively prior to the date of site initiation (Cohort 1); however, if the target sample size is not met, then a second Cohort of patients will be initiated after the site initiation date (Cohort 2).

#### Cohort 1:

The study will involve collection of pre-defined, structured data retrospectively from medical records (electronic and/or paper if necessary) of patients who meet the study eligibility criteria (see Section 3.1.2) and who have been prescribed nirmatrelvir, ritonavir treatment within a 15-month lookback period from the date of site initiation (Cohort 1). The lookback period will span from 01 April 2022 to 30 June 2023. Data abstracted from patients' medical records will include patient demographics and clinical characteristics at index date (defined as the date of nirmatrelvir, ritonavir treatment prescribing), in addition to patients' HCRU during the 30-day period post-index date.

#### Cohort 2:

If the minimum target sample size of 250 patients is not achieved from Cohort 1, then a second Cohort of patients (Cohort 2) will be initiated and will be included in the study until the target sample size is met. Cohort 2 patients are those who meet the eligibility criteria (see Section 3.1.2), and who have been prescribed nirmatrelvir, ritonavir treatment after the date of site initiation. As for patients in Cohort 1, the following data will be collected for patients in Cohort 2: demographics and clinical characteristics at index date, and HCRU during the 30day period post-index date.

Patients in Cohort 1 will be enrolled in the study in a consecutive manner from start of site initiation till lookback period until we reach desired sample size, in case the number of eligible patients is significantly larger than the sample size. For Cohort 2, patients will be enrolled in the study in a consecutive manner from start of site initiation until we reach desired sample size. *An electronic Case Report Form (eCRF) will be available for* 

PFIZER CONFIDENTIAL CT24-WI-GL03-RF03 2.0 Non-Interventional Statistical Analysis Plan 01-Jun-2020 Page 10 of 42 the selected sites to fill in for each patient included in Cohort 1 or Cohort 2. Patient data will be extracted from the medical records and entered into the eCRFs by trained site study personnel. Participation in this study is not intended to change the routine treatment patients receive, as determined by their prescribing physicians; all treatment decisions, type and timing of the disease monitoring are per routine clinical care, and at the discretion of the treating physician and patient.

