#### 9. RESEARCH METHODS

#### 9.1. Study Design

This is a multi-center, retrospective observational study that will be conducted in KSA. The aim of this study is to capture data on the baseline demographic, clinical characteristics, and HCRU of adult COVID-19 patients who have been prescribed nirmatrelvir, ritonavir treatment.

An overview of the study design is depicted in Figure 1. The sample size for this study depends on the number of COVID-19 patients visiting the selected sites, in addition to nirmatrelvir, ritonavir prescription practices by the treating physician in line with local prescription guidelines in KSA. However, based on feasibility assessments, the minimum target sample size for the study is approximately 500 evaluable patients across 3 sites in KSA. The study will aim to meet this target sample size with a single cohort of patients identified retrospectively prior to the date of site initiation (Cohort 1); however, if the target sample size is not met, then a second cohort of patients will be initiated after the site initiation date (Cohort 2).

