# Cohort 2:

If the minimum target sample size of 500 patients is not achieved from Cohort 1, then a second cohort of patients (Cohort 2) will be initiated and will be included in the study until the target sample size is met. Cohort 2 patients are those who meet the eligibility criteria (see Section 9.2.1), and who have been prescribed nirmatrelvir, ritonavir treatment after the date of site initiation. As for patients in Cohort 1, the following data will be collected for patients in Cohort 2: demographics and clinical characteristics at index date, and HCRU during the 30-day period post-index date.

Patients in Cohort 1 will be enrolled in the study either in a sequential manner or selected via computer-generated random allocation in case the number of eligible patients is significantly larger than the sample size. For Cohort 2, patients will be enrolled in the study in a sequential manner. An electronic Case Report Form (eCRF) will be available for the selected sites to fill in for each patient included in Cohort 1 or Cohort 2. Patient data will be extracted from the medical records and entered into the eCRFs by trained site study personnel. Participation in this study is not intended to change the routine treatment patients receive, as determined by

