#### Figure 1. Study Design

#### 3.1.1 Study population

Data will be collected for all eligible adult COVID-19 patients who have been prescribed nirmatrelvir, ritonavir across 3 selected sites in KSA which are National Guard Hospital-Riyadh, King Faisal Specialist Hospital-Riyadh and King Faisal Specialist Hospital-Jeddah. These 3 healthcare centers are the largest COVID-19 care providers in KSA representing the majority of COVID-19 patients who have been prescribed nirmatrelvir, ritonavir at the national level. In addition, these three healthcare centers have the same guidelines for treatment and management of patients with COVID-19.

The selected sites with well-established clinical research infrastructures, are situated in the major cities of KSA, where COVID-19 patients are most prevalent. They provide medical attention to any COVID-19 patient and provide healthcare to complicated patients, including immunocompromised patients.

These facilities also maintain patient records and have access to electronic medical records for patient data retrieval.

The minimum target sample size is 250 patients. Patient eligibility will be assessed at patient index date. Patients in Cohort 1 will be identified during a 15-month lookback period prior to the date of site initiation, and patients in Cohort 2 will be identified

PFIZER CONFIDENTIAL CT24-WI-GL03-RF03 2.0 Non-Interventional Statistical Analysis Plan 01-Jun-2020 Page 11 of 42 following the date of site initiation if the minimum target sample size for the study is not achieved from Cohort 1.

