#### Limitations and Bias

As this is a retrospective observational study and participant enrolment in the study will be done in a consecutive manner. This approach is associated with low possibility of bias and representativeness of the enrolled sample could be affected, if there is pattern observed among a particular age group or due to any season etc. In case such selection bias is observed, then additional stratification/ subgroup can be reported in the analysis, as required.

Since this study will involve collection of existing data from medical records, misclassification bias due to recording errors is possible. Medical records may not always be complete, the availability and quality/completeness of data may vary

> PFIZER CONFIDENTIAL CT24-WI-GL03-RF03 2.0 Non-Interventional Statistical Analysis Plan 01-Jun-2020 Page 23 of 42

considerably between different sites within KSA, and there may be abstraction errors and differences in reporting standards between the different sites.

Another limitation to be considered is the characteristics of the patient population to be included in the final analysis, which may potentially be biased based on the KSA national recommendations put in place for the management and treatment of COVID-19 during the observational period. This may affect the generalizability of findings from this study across different countries in the real-world setting.

At the patient-level, misclassification of drug exposure has to be considered. Medical records provide detailed information on patient demographics, clinical characteristics, and prescribed nirmatrelvir, ritonavir treatment, but may not contain information on the intended duration of use (days of supply) and may not contain accurate information on the actual treatment pattern of nirmatrelvir, ritonavir medications by the patient ie, patient adherence (if any).

COVID-19 outcomes are dependent on individuals seeking healthcare i.e., individual may have symptoms for long but if there is not an interaction with the health system, it will be unknown.

Number	Description					
Table shells for P	Table shells for Primary objectives					
Table shell 1	Summary of patient enrolment at Index date.					
Table shell 2	Summary of demographic characteristics of patients at Index date.					
Table shell 3	Summary of clinical characteristics of patients at Index date.					
Table shell 4	Summary of COVID-19 vaccination history of patients at Index date.					

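### If eligible patients exceed the target, the SAP fills Cohort 1 consecutively instead of by the protocol's random draw, so only part of the 15-month lookback would be sampled

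*SAP*

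**What the plan says.** Both documents give the Cohort 1 enrolment rule in the paragraph under the Cohort 2 heading.

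- **Protocol 9.1.** Cohort 1 is enrolled sequentially or "selected via computer-generated random allocation in case the number of eligible patients is significantly larger than the sample size".
- **SAP 3.1.** Cohort 1 is enrolled "in a consecutive manner from start of site initiation till lookback period until we reach desired sample size", and this is tied to the condition "in case the number of eligible patients is significantly larger than the sample size". The random option is gone.
- **Window.** "The lookback period will span from 01 April 2022 to 30 June 2023" (SAP 3.1, Cohort 1; the protocol has the same dates).
- **Target.** The protocol says "the minimum target sample size for the study is approximately 500 evaluable patients across 3 sites in KSA"; the SAP says "the minimum target sample size for the study is approximately 250 evaluable patients across 3 sites in KSA". Each is a single total with no allocation by site or calendar period.
- **Bias statement.** SAP Section 8 says of consecutive enrolment: "This approach is associated with low possibility of bias". It goes on to concede that patterns by age group or season could affect representativeness, and allows further strata if such bias is seen.

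The SAP change log covers the new selection method with one short entry against Section 3.1 (version 1.2, 26 July 2023) and gives no reason. The sample-size update is logged only in version 2.0 (16 September 2024).

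**The concern.** The primary objective is purely descriptive: who was prescribed the drug at these centres during the lookback. There is no comparison to protect, so validity rests on whether the enrolled patients represent that population.

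The protocol foresaw that there might be more eligible patients than needed and provided a random draw for that case. The SAP keeps the same trigger but attaches a rule that starts at one end of the window and stops once enough patients are in. Prescriptions beyond the stopping point then have no chance of selection.

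Several of the planned summaries in SAP 7.2 can move with calendar time: time since vaccination, number of doses, previous infection and variant. A time-truncated sample describes these for the sampled months only, while the tables would be read as describing April 2022 to June 2023.

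**Working it through.** **1. Window.** April to December 2022 is 9 months (275 days) and January to June 2023 is 6 months (181 days). Together they make 15 months (456 days), which agrees with the stated lookback. The targets of 500 and 250 rest on feasibility, with no formula, so there is no sample-size figure to reproduce.

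**2. Inclusion probabilities when the eligible count E exceeds the target T.**

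- Protocol's random draw: T/E for every eligible prescription, whatever its date.
- SAP's consecutive rule: 1 inside the block that is reached, 0 outside it.

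Read naturally, the SAP sentence runs backward from site initiation, so the early months are lost. If a forward direction was meant, the late months are lost. Either way the sample is one contiguous block.

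**3. Months covered.** E is not in the documents. Assume prescriptions are spread evenly over the window and sites work through it at the same pace. Then months covered = 15 × min(1, T/E).

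| E (assumed) | T = 500 (protocol) | T = 250 (current SAP) |
|---|---|---|
| 300 | 15 | 12.5 |
| 500 | 15 | 7.5 |
| 750 | 10 | 5 |
| 1000 | 7.5 | 3.75 |
| 1500 | 5 | 2.5 |

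Filling backward from 30 June 2023, 7.5 months is 228 days and reaches to about 15 November 2022; 3.75 months is 114 days and reaches to about 9 March 2023.

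Both columns are needed. The consecutive rule entered in July 2023 and the log shows no change of sample size before September 2024. Protocol Section 6 planned data collection from 01 July 2023 to 01 February 2024, so the target in force during planned abstraction was presumably 500.

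**4. Effect on a reported proportion.** Let f = T/E be the sampled fraction, and let p_in and p_out be the proportions in the sampled and unsampled months. The sample estimates p_in. The 15-month value is f·p_in + (1 − f)·p_out. The difference is (1 − f)(p_in − p_out). At f = 0.5 half of any change over time passes into the estimate; at f = 0.25 three quarters does; at f = 1 none does. The documents give no basis for a value of p_in − p_out.

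**5. Can later stratification repair it?** No. Strata within the sample cannot supply p_out when the sample holds no patients from those months.

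**The case against.** The strongest reply is that the trigger may never have been met. The target was halved in SAP version 2.0, after the planned end of data collection and after some analyses had been run (the log says so for the additions in Section 7.3). That fits a shortfall better than an excess. If all eligible patients were enrolled, the rule had no effect. This stands as a limit on the finding, but the documents do not settle it, and the current SAP still contains the rule.

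Other points on that side:

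- The protocol also allowed sequential enrolment, and its Section 9.8 lets the SAP modify its plans. Both are true. Random selection was nevertheless the protocol's provision for the excess case, which is exactly where the SAP now puts consecutive filling.
- SAP Section 8 partly discloses the risk by naming season. It does not say that whole months may be missing, and its remedy cannot reach them.
- Both targets are minima, and the SAP does not define its desired size as a cap. That adds uncertainty about where the rule stops; it does not remove the truncation.
- The SAP sentence does not state its direction plainly, and it cites sources not available here.

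Three stronger readings are tempting and should not be drawn:

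- **That the enrolled sample is in fact the most recent prescriptions.** This follows only if the excess condition held.
- **That the fastest-abstracting sites dominate.** Neither document mentions abstraction speed or site shares. A single pooled total makes site imbalance possible, but the protocol's random option sets no site allocation either.
- **That the rule creates the conflict with the SAP 3.1.1 statement "Data will be collected for all eligible adult COVID-19 patients who have been prescribed nirmatrelvir, ritonavir across 3 selected sites in KSA".** Protocol 9.2 makes essentially the same statement alongside random selection. Any subsampling conflicts with it.

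**Conclusion.** The point holds conditionally. In the excess case the SAP replaces a selection method that represents the whole lookback with one that samples a single contiguous part of it, and its low-bias statement is then not justified.

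The size depends on an eligible count that the documents do not give. It is nil when that count is at or below the target. Under an even prescription rate, 1000 eligible patients would leave 7.5 of 15 months unsampled at a target of 500, or 11.25 of 15 (15 − 3.75) at 250. With 500 eligible, nothing is lost at 500 and 7.5 months are lost at 250. The resulting bias in any characteristic also depends on how much that characteristic changed over the window, which is unknown.

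The contradiction between protocol and SAP is certain. Whether it affected the data is not known. It should be corrected or closed by reporting.

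**What to change.** **If abstraction is not complete,** replace the Cohort 1 sentence in SAP 3.1 with wording such as:

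> Each site lists every eligible prescription with an index date from 01 April 2022 to 30 June 2023. If the listed total exceeds the target, Cohort 1 is drawn from the lists by computer-generated random selection over the whole period; otherwise all listed patients are enrolled.

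State the target as a number. Allocation proportional to the eligible count by site and calendar quarter is an optional refinement that the protocol does not require. The cost is a list per site and one random draw; the number of patients does not rise.

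**If abstraction already followed the consecutive rule,**

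- add to Table shell 1 the eligible and enrolled counts and the index-date range covered, by site;
- limit the primary description to that range;
- replace the low-bias statement in SAP Section 8 with a plain statement of the time truncation.

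The cost is a count of eligible prescriptions at each site and a few lines of text. A fresh random draw at this stage would mean abstracting further records and is not asked for.

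**If all eligible patients were enrolled,** say so in the SAP and the report. The counts in Table shell 1 will show it, and the point is closed.
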